**Table 1: Planned Doses to Be Administered for Part 1**

Cohort	Dosing Days	Muscle	Planned Dose Level	Type of Administration	ACE-083 n
1a	1, 22, 43, 64, and 85	Tibialis Anterior	150 mg	Unilateral	6
2a	1, 22, 43, 64, and 85	Tibialis Anterior	200 mg	Unilateral	6
3a	1, 22, 43, 64, and 85	Tibialis Anterior	200 mg	Bilateral	6
Total Number of Patients (Planned)					18

Cohort	Dosing Days	Muscle	Planned Dose Level	Type of Administration	ACE-083 n
1b	1, 22, 43, 64, and 85	Biceps brachii	150 mg	Unilateral	6
2b	1, 22, 43, 64, and 85	Biceps brachii	200 mg	Unilateral	6
3b	1, 22, 43, 64, and 85	Biceps brachii	240 mg	Unilateral	6
Total Number of Patients (Planned)					18

Periodic reviews of selected blinded safety and imaging data will be reviewed by the Safety Review Team (SRT) in accordance with the SRT Guidelines.

### 3.2. Part 2

Prior to the initiation of Part 2, a review of the safety and efficacy data from Part 1 will be done in order to determine whether one or both the TA and BB muscles will be studied as well as the recommended dose level for each muscle. Up to 56 patients (28 patients per muscle) will be enrolled and randomized (1:1 ratio) to receive either ACE-083 (n=14/muscle) or placebo (n=14/muscle) bilaterally to either the TA or BB muscles (but not both). Patients will receive study drug once every three weeks for approximately 6 months (9 doses). If a patient discontinues the study for reasons other than a safety issue related to investigational study drug and the patient had not completed the Day 43 visit, the patient may be replaced. The replacement patient will receive the same treatment as the patient replaced.

Patients who complete the double-blind treatment period will immediately roll over to open-label treatment with ACE-083. All patients will receive ACE-083 administered at the same dose as in the double-blind period. They will receive bilateral injections, in the same muscles that study drug was administered to during the double-blind period, once every three weeks for approximately 6 months (8 doses). In Part 2, the SRT will periodically review blinded safety data for each muscle treated.

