#### 4.1.1. Sample Size Determination

There was no formal sample size calculation for Part 1. Six patients in each cohort will provide sufficient data to evaluate safety and a preliminary assessment of changes in muscle volume and muscle strength.

The sample size calculation for Part 2 is based upon the percent change from baseline in total muscle volume of the injected TA muscle 3 weeks after the last dose. A 10% difference between ACE-083-treated and placebo groups in the percent change in total muscle volume from baseline is considered to be clinically meaningful. The standard deviation (SD) is assumed to be approximately 9% for each group, based on preliminary MRI data for the ACE-083-treated side from the initial TA cohort in Part 1. Similar assumptions apply for the treatment of the BB muscle.

Assuming a 2-sided type I error rate of 0.10, a 10% difference in percent change from baseline between ACE-083-treated and placebo groups in total muscle volume, a standard deviation of 9% for each group, and a 1:1 randomization, 83% power is achieved with a total sample size of 24 for the TA muscle (12 active, 12 placebo), based on a standard t-test.

In addition, this sample size also provides 83% power to detect a 10% difference in 6-minute walk test distance, based on a similar estimated SD of 9% and a 2-sided type 1 error rate of 0.10.

In order to account for dropouts (up to 15%), 28 patients will be randomized to study treatment for each muscle (14 active, 14 placebo) to ensure that at least 12 patients per treatment group complete the double-blind treatment period.

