#### 4.1.3. Treatment Description

Treatment descriptions as well as abbreviations used in tables, listings, and figures are described below:

##### Part 1

Unless otherwise stated, tables and figures will be presented as shown below:

Part 1 – Tibialis Anterior

ACE-083 150 mg Unilateral	ACE-083 200 mg Unilateral	ACE-083 200 mg Bilateral	Overall
------------------------------	------------------------------	-----------------------------	---------

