### **Motor Function Variables**

Individual motor function data will be listed.

For motor function test variables (TA cohorts: cumulative distance at 6 minutes from the 6-minute walk test, time to complete 10 meter walk/run test, 4-stair ascend time, 4-stair descend time, gait parameters; BB cohorts: PUL parameters) the raw data as well as absolute and percent change from baseline will be provided.

Least square mean estimates of the effect of ACE-083 and corresponding 90% and 95% confidence intervals will be produced for the percent change data at 3 weeks post last dose described above using an ANCOVA with BASELINE, COHORT, and BASELINE\* COHORT as covariates where:

- BASELINE represents the baseline value of the parameter of interest
- COHORT represents the dose level of ACE-083 administered to the muscle
- BASELINE\*COHORT represents the interaction of BASELINE and COHORT

Additional analyses may be performed as appropriate.

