### **Patient reported outcome variables**

Individual FSHD-HI scored data (total score and each of the subscale scores) will be listed.

Descriptive statistics of the raw data as well as for the absolute and percent change from baseline will be provided for the FSHD-HI total score as well as for each of the subscale scores.

Least square mean estimates of the effect of ACE-083 and corresponding 90% and 95% confidence intervals will be produced for the absolute change data at 3 weeks post last dose described above using an ANCOVA with BASELINE, COHORT and BASELINE\*COHORT as covariates where BASELINE, and COHORT are defined similarly as described above for other analyses.

Additional analyses may be performed as appropriate.

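### The Part 1 motor-function and FSHD-HI ANCOVAs define COHORT as dose level, so the TA model as written cannot separate 200 mg unilateral from 200 mg bilateral

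*SAP*

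**What the plan says.** SAP Table 1 (Section 3.1) plans three TA cohorts of six: 1a at 150 mg unilateral, 2a at 200 mg unilateral and 3a at 200 mg bilateral. The three biceps brachii (BB) cohorts are all unilateral, at 150, 200 and 240 mg. SAP 4.1.3 gives the two 200 mg TA cohorts their own default columns, "ACE-083 200 mg Unilateral" and "ACE-083 200 mg Bilateral".

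For MRI and strength, SAP 4.7.2.1 separates the cohorts by mode of administration. The ANCOVA with COHORT as dose level stands under the unilateral cohorts and is fitted separately for TA and BB. The bilateral cohort has its own one-sample t-test.

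For motor function the scope is wider: "For motor function test variables (TA cohorts: cumulative distance at 6 minutes from the 6-minute walk test, time to complete 10 meter walk/run test", followed by the other TA tests and, for BB, the PUL. Least squares (LS) means and confidence intervals "will be produced for the percent change data at 3 weeks post last dose described above using an ANCOVA with BASELINE, COHORT" and the baseline-by-cohort interaction. The definition repeats the one in the unilateral model: "COHORT represents the dose level of ACE-083 administered to the muscle". This subsection has no restriction to unilateral cohorts, no term for mode of administration and no separate bilateral analysis. The FSHD-HI subsection then says that "BASELINE, and COHORT are defined similarly as described above for other analyses".

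**The concern.** Within one muscle, dose level identifies each unilateral cohort uniquely, so the definition works for the MRI and strength ANCOVA. Once the bilateral TA cohort enters the same model it no longer works, because 2a and 3a have the same dose per muscle. A programmer who follows the text puts both cohorts into one level, with one intercept and one baseline slope.

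The outcomes concerned are the walk tests, stair climb, gait and FSHD-HI, which are measured on the whole patient and not on one side. Injecting one leg and injecting both may therefore have different effects on them. A combined 200 mg estimate would describe a mixture of the two regimens. The model would also contain nothing to show whether they differ.

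The definition also conflicts with the display plan. SAP 4.1.3 sets two 200 mg TA columns, and a dose-level factor yields one 200 mg LS mean. One of the two instructions has to be set aside at programming, and the SAP does not say which.

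**Working it through.** **Inputs.** Cohort sizes, doses and administration: SAP Table 1. Model terms and the COHORT definition: SAP 4.7.2.1, Motor Function Variables and Patient reported outcome variables. Display columns: SAP 4.1.3.

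**The plan's own figure.** Planned TA patients in Part 1: 6 + 6 + 6 = 18, which agrees with Table 1.

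**Levels and degrees of freedom, TA motor function.** Baseline, cohort and their interaction give one intercept and one slope per COHORT level, so parameters = 2 × levels and residual df = 18 − parameters.

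| COHORT coded as | Levels (n) | Parameters | Residual df |
|---|---|---|---|
| Dose level, as written | 150 mg (6), 200 mg (6 + 6 = 12) | 2 × 2 = 4 | 18 − 4 = 14 |
| Table 1 cohort | 1a (6), 2a (6), 3a (6) | 3 × 2 = 6 | 18 − 6 = 12 |

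A check of the design-matrix ranks gave the same counts (rank 4 and rank 6). Only the second coding produces the two 200 mg estimates that SAP 4.1.3 displays.

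**What the combined 200 mg estimate represents.** Let *u* and *b* be the mean changes in 2a and 3a. With equal numbers and similar baselines:

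- combined estimate ≈ (6*u* + 6*b*)/12 = (*u* + *b*)/2
- distance from each cohort's own value ≈ |*b* − *u*|/2

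The documents give no value for *b* − *u*. Assumed differences, for illustration only:

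| Assumed difference (percentage points) | Combined estimate differs from each cohort by about |
|---|---|
| 0 | 0 |
| 5 | 2.5 |
| 10 | 5 |

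If baselines differ between 2a and 3a, the adjusted value need not be the midpoint. The common 200 mg slope would then also absorb part of the cohort difference.

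**BB motor function.** The doses are 150, 200 and 240 mg, all different and all unilateral. Both codings give the same three levels.

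**FSHD-HI.** This subsection inherits the definition, has no muscle term and does not say that TA and BB are fitted separately, as the MRI and strength subsection does. If fitted separately, the TA model has the two-level problem above and BB does not. Read literally as one model, the dose-level factor would combine 1a with 1b at 150 mg (6 + 6 = 12), and 2a, 3a and 2b at 200 mg (6 + 6 + 6 = 18), leaving 3b alone at 240 mg (6).

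**The case against.** The strongest reply is that three levels were probably intended. The term is called COHORT, Table 1 lists 1a, 2a and 3a separately, and the default columns keep them apart. No sentence says that 2a and 3a are to be pooled. A reader might infer a deliberate decision to pool them. The documents do not support that: the sentence repeats the one in the unilateral model and looks carried over. This bears on intent, but the written definition is explicit and still gives two levels.

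The reply is also right that the bilateral results stay visible. Individual data are listed. Part 1 descriptives for gait, the walk tests and the stair climb are planned by cohort, and SAP 4.1.3 gives 3a its own column by default.

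A reader might infer further that losing the 3a estimate harms the choice of muscle or dose for Part 2, where dosing is bilateral. The documents do not support this either. Motor function and FSHD-HI are exploratory in Part 1 (SAP 2.3; Protocol Section 6). Protocol 14.2.3.3 plans descriptive summaries for them, with other analyses as appropriate. The move to Part 2 rests on a review of Part 1 safety and efficacy data and on Safety Review Team recommendations (Protocol 7.1, 10.2, 14.2), and no passage ties it to this ANCOVA.

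Finally, 3a need not be purely bilateral. Protocol 10.1 allows a patient in a bilateral Part 1 cohort whose other side is grade 5 to be injected on the weak side only. Recoding by cohort alone would therefore not fully separate one-leg from two-leg treatment. This stands, and the fix has to address it.

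**Conclusion.** The point holds as a definition error of limited reach. Followed as written, the Part 1 TA motor-function ANCOVA has two COHORT levels instead of three. Its single 200 mg LS mean rests on 12 planned patients, six from each regimen, and cannot fill the two 200 mg columns. The FSHD-HI ANCOVA inherits the definition and also leaves open whether the muscles are modelled separately.

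The affected quantities are exploratory LS means with their 90% and 95% confidence intervals. The by-cohort descriptives, the MRI and strength analyses, BB motor function and all Part 2 analyses are unaffected.

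The distortion cannot be sized from the documents. It is zero if unilateral and bilateral dosing have the same effect, and about half the difference if cohort sizes and baselines are similar. A fixed percentage understatement of the bilateral effect would require an assumed ratio between the two effects, and the documents give none.

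**What to change.** In the Motor Function Variables and Patient reported outcome variables subsections of SAP 4.7.2.1:

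- Define COHORT as the Table 1 cohort, that is, dose level together with unilateral or bilateral administration, so that the TA model has levels 1a, 2a and 3a and matches the columns in SAP 4.1.3.
- State that the FSHD-HI model is fitted separately for TA and BB.
- State how a patient enrolled in a bilateral cohort but injected on one side only is classified in these analyses.

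The MRI and strength text can stay, because it already separates the unilateral cohorts from the bilateral one.

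The edit is a few phrases, and no new displays or data are needed. The statistical cost in the TA model is two residual degrees of freedom, 12 instead of 14 on 18 planned patients. Each 200 mg estimate would then rest on six patients instead of twelve, so its interval may be wider, but it would refer to one cohort.

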### **Patient reported outcome variables**

Individual FSHD-HI scored data (total score and each of the subscale scores) will be listed.

Descriptive statistics of the raw data as well as for the absolute and percent change from baseline will be provided for the FSHD-HI total score as well as for each of the subscale scores.

Least square mean estimates of the effect of ACE-083 and corresponding 90% and 95% confidence intervals will be produced for the absolute change data at 3 weeks post last dose described above using an ANCOVA with BASELINE, COHORT and BASELINE\*COHORT as covariates where BASELINE, and COHORT are defined similarly as described above for other analyses.

Additional analyses may be performed as appropriate.

### **Gait**

Individual data will be listed.

Descriptive statistics will be provided for each type of measurement recorded (i.e. “General measures”, “Initial measures”, “Peak measures”, and “Average measures”) by cohort and scheduled time.

For gait assessments that are reported in triplicates at a given visit for any patient and are assessed to be of good quality, the mean of these will be used for purposes of generating a single individual value for the patient at the scheduled visit which will then be summarized.

In addition, “Stride Length” will be derived using the following formula:

$$\text{Stride Length (m)} = \{\text{Mean of the triplicate measures of Left Step Length (m)}\} + \{\text{Mean of the triplicate measures of Right Step Length (m)}\}$$

Additional analyses may be performed as appropriate.

#### 4.7.2.2. Part 2

##### **Primary Efficacy Analysis (Double-Blind Phase)**

###### **MRI: Total Muscle Volume**

Individual total muscle volume data will be listed. Descriptive statistics will be provided by treatment group and scheduled time for raw data and changes from baseline (absolute and percent change). Absolute and percent changes from baseline will be provided for each side (left and right) as well as the average of the absolute change and average of the percent change for the left and right sides. This will be done for the double-blind, placebo-controlled component as well as for the open-label component.

For the double-blind component, the plot of mean ( $\pm$  SEM) for the average of left and right side percent change in total muscle volume from baseline by scheduled day and treatment group for each muscle group (BB and TA) during the double-blind period as well as during the open-label extension period will be provided.

For the double-blind component, an ANCOVA model will be fitted in order to assess the effect of ACE-083 on the Day 190 average percent change from baseline in total muscle volume for the left and right sides. Covariates to be included in the model are MUSCLE, TREATMENT, BASELINE, MRC-MMT GRADE CATEGORY, MUSCLE\*TREATMENT, and BASELINE\*MUSCLE where:

- MUSCLE represents the muscle treated (BB or TA)
- TREATMENT represents the treatment group (ACE-083 or placebo)
- BASELINE represents the baseline total muscle volume (average of left and right sides)
- MRC-MMT GRADE CATEGORY represents the randomization stratification factor (3 to 4- or 4- to 4+)
- MUSCLE\*TREATMENT represents the muscle-by-treatment interaction
- BASELINE\*MUSCLE represents the baseline-by-muscle interaction

The effect of ACE-083 on the percent change in TMV from baseline of the injected TA or BB at Day 190 versus placebo will be estimated using the ANCOVA model described above and tested using a 0.1 significance level (2-sided) separately for TA and BB. The least squares mean estimate along with the corresponding 90% confidence interval will be provided separately for TA and BB. In addition, the 95% confidence interval will also be provided as well as a bar chart

of the least squares mean estimates ( $\pm$  SEM) for each of the treatment groups separately for TA and BB.

A mixed model repeated measures (MMRM) analysis will be performed to assess the sensitivity to the ANCOVA analysis described above. An unstructured covariance structure will be used to model the within-patient covariance across visits. Other covariance structures will be considered if the unstructured covariance fails. The covariates to be included consist of all of the covariates described above for the ANCOVA with the addition of the following additional covariates: VISIT where VISIT represents the scheduled visit day post first dose of MRI assessment (D43, D106, D190), MUSCLE\*VISIT, TREATMENT\*VISIT, and MUSCLE\*TREATMENT\*VISIT.

For both the ANCOVA and MMRM analyses, multiple imputations will be performed for missing data. Twenty imputations will be performed. The seed to be used is specified in Section 5. The assumption of the missing data mechanism will be missing at random (MAR) unless the data suggest otherwise. The missing data pattern (monotone or arbitrary) will also be evaluated and the regression method for imputing missing data will be utilized for each scheduled timepoint with missing data. Covariates to be included when imputing missing data include: MRC-MMT GRADE CATEGORY, TREATMENT, BASELINE, MUSCLE\*TREATMENT, and TMV percent change data at scheduled timepoints prior to the timepoint at which TMV percent change is being imputed.

The table below illustrates the covariates that should be used for imputing missing data:

Data to be Imputed	Covariates to use in Multiple Imputation Regression Model
Baseline TMV	MRC-MMT GRADE CATEGORY, MUSCLE, TREATMENT, MUSCLE*TREATMENT
Day 43 Percent change in TMV from baseline	MRC-MMT GRADE CATEGORY, MUSCLE, TREATMENT, MUSCLE*TREATMENT, BASELINE
Day 106 Percent change in TMV from baseline	MRC-MMT GRADE CATEGORY, MUSCLE, TREATMENT, MUSCLE*TREATMENT, BASELINE, Day 43 TMV percent change
Day 190 Percent change in TMV from baseline	MRC-MMT GRADE CATEGORY, MUSCLE, TREATMENT, MUSCLE*TREATMENT, BASELINE, Day 43 TMV percent change, Day 106 TMV percent change

Analysis findings will be presented for Day 190 percent change data where missing data is not imputed (observed data) as well as for Day 190 percent change data where multiple imputations are performed for missing data to assess the impact of the missing data on the observed study data. The analyses where multiple imputations are performed are considered to be primary.

For BB patients, the above analyses will be repeated using the patient's "preferred" side used for the PUL test for patients.

The Per Protocol Set will be used for the primary analysis. The analyses described above will also be repeated for the Full Analysis Set.

Additional analyses may be performed as appropriate.

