Per Protocol Set: All patients enrolled/randomized in the study, who have received at least one dose of study drug (including placebo) with no major protocol violations and at least one post-baseline efficacy evaluation

Pharmacokinetics Population: All patients who have received at least one dose of study drug and have sufficient PK samples collected and assayed for PK analysis

Statistical Analysis:

Complete details regarding the statistical analyses outlined below will be presented in a separate statistical analysis plan. For statistical analyses involving safety data, these will be done on the safety population. For statistical analyses involving pharmacokinetic data, these will be done on the pharmacokinetics population. For statistical analyses involving efficacy and/or pharmacodynamics data, these will be done using the full analysis set and per protocol set populations.

Part 1: Safety, pharmacodynamic and efficacy data will be summarized by cohort. For each efficacy parameter, the absolute and percent change from baseline in the injected TA or BB and, with the exception of motor function tests and FSHD-HI total score and subscale score data, the raw and percent change from baseline of the treated, untreated, and treated minus untreated TA or BB muscle will be presented over time for patients receiving unilateral dosing of ACE-083.

For efficacy measurements that are collected multiple times during the 1-month screening period, changes observed during this time will serve as the control for each patient. They will be summarized together with post-baseline data.

Part 2: The primary efficacy parameter will be the percent change in total muscle volume from baseline of the injected TA or BB 3 weeks after the last dose of the double-blind treatment period. A repeated measures analysis of covariance model will be used to compare the two treatment groups (ACE-083 and placebo) using a 2-sided 0.10 significance level. If the 3-week post last dose data from the double-blind treatment visit are missing, the last observation will be carried forward. Additional techniques for handling missing data will also be evaluated as sensitivity analyses to the last observation carried forward approach.

Other strength and functional measurements will be tested similarly. Estimates of the effect of ACE-083 and corresponding 90% confidence intervals will be produced.

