10.5. Randomization and Blinding

Part 1: This is an open-label, dose escalation phase that does not require randomization.

If a patient discontinues the study for reasons other than a safety issue related to ACE-083 and the patient had not completed the Day 43 visit, the patient may be replaced. The replacement patient will receive the same treatment as the patient replaced. Both the replacement and originally allocated patient numbers will be unique numbers.

Part 2: Patients who have signed the informed consent and meet all eligibility criteria will be stratified by baseline MRC MMT grade (3 to 4- and 4- to 4+) of the weaker side and then randomized to receive ACE-083 (at a dose level determined by Part 1) or placebo. Patients with a MRC MMT grade 4-may be stratified with either grade 3 to 3+ patients or 4 to 4+ patients depending on the computer-generated randomization scheme. These patients will only be included in the stratum assigned during randomization. The randomization scheme will be computer generated and will be prepared by a statistical group designated by the sponsor. If a patient discontinues the study for reasons other than a safety issue related to ACE-083 and the patient had not completed the Day 43 visit, the patient may be replaced. The replacement patient will receive the same treatment as the patient replaced. Both the replacement and originally allocated patient numbers will be unique numbers.

Among study personnel, only the pharmacist or his/her designee who prepares the study drug (ACE-083 or placebo), an unblinded clinical monitor designated by the sponsor, and the analytical laboratory will be unblinded to the patient treatment assignments. All other study personnel (including but not limited to investigators, study coordinators, nursing staff, and clinical monitors) and all patients will remain blinded to the study treatment assignments. The sponsor and the sponsor's representatives will also remain blinded to the study treatment assignments.

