⁸ Vital signs (weight, heart rate, systolic and diastolic blood pressure) must be taken prior to administration of study drug on dosing days. Height is collected only at screening.

⁹ Tests defined in [Appendix 2, Table 7](#).

¹⁰ PK samples on a dosing day have a \pm 15 minute window for post-dose sample collection, based on the time of the first injection. Pre-dose samples may be collected up to 4 hours prior to dosing. Day 2 and 86 sample collection should be 24 hours post dose \pm 3 hours.

¹¹ MRI assessments should be completed within 5 days prior of the scheduled dose administration. MRI assessments during the follow up period (Day 358/ET and Day 393/EOS) have a \pm 5 day window

¹² Maximum voluntary isometric contraction testing (MVICT) of both TA and BB muscles will be conducted for all cohorts at screening visits, Day 190 and Day 393/EOS. At all other visits, only the muscle under study will be tested (i.e., TA or BB). Both sides will be tested for all visits (right and left).

¹³ TA cohort only: 10-meter walk/run, 4-stair climb, 6-minute walk test, and gait analysis are performed at all visits: 100-meter timed test begins at Day 169 and continues throughout open-label visits; lower leg assessments will be collected for the BB cohorts at screening visits, Day 190 and Day 393/EOS only.

¹⁴ BB cohort only: PUL mid-level/elbow dimension performed at all visits; additional PUL high level/shoulder dimension begins at Day 169 and continues throughout open-label visits; PUL testing will also be performed on patients in TA cohorts at screening visits (mid level), Day 190 (high and mid-level) and Day 393/EOS (high and mid-level) only.

Non-ambulatory patients in the BB cohort can opt out of the TA assessments.

¹⁵ Randomization should occur within 24 hours prior to Day 1 dose.

¹⁶ Study drug administration should occur within 21 days (\pm 3 days) of the last dose.

¹⁷ Patients who discontinue prior to the Day 358/ET visit should complete the Day 358/ET visit at the time of discontinuation and return for the remaining follow-up period visit. If an MRI has been completed within 4 weeks of discontinuation, it does not need to be repeated as part of the Day 358/ET visit procedures.

¹⁸ If a patient has a positive ADA result at Day 393/EOS, the patient will be asked to return to the clinical site for additional follow-up approximately every 3 months until a negative or stable result is obtained.

¹⁹ ECG is to be conducted \pm 1 hour of the 4h PK sample.

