## 4.2. Analysis Population

The analysis populations include the following:

- Full Analysis Set: Part 1 – All patients enrolled in the study receiving at least one dose of ACE-083. Part 2 – All patients randomized;
- Safety Set: All patients enrolled/randomized in the study who have received at least one dose of study drug (includes placebo);
- Per Protocol Set: All patients enrolled/randomized in the study who have received at least one dose of study drug (includes placebo) with no major protocol violations.
  - Major protocol violations include:

- Patients who discontinue the study prior to the Cycle 3 Day 43 visit; these patients are replaced per protocol
- Patients whose Day 1 MRI or Day 190 MRI was done 7 or more days following study drug administration
- Patients whose functional assessments (i.e. 10mW/R, mid-level PUL, 6MWT, 4-stair climb) at Day 1 or Day 190 were done 7 or more days following study drug administration
- Patients who did not receive the full study drug administration planned per protocol at all injection sites on any or both sides (right or left) for 2 or more consecutive visits for reasons other than dose reductions for the safety of the patient or feasibility concern (i.e., the site intended to administer the full dose but was unable).

Should the statistical analysis populations be identical (e.g., Full Analysis Set = Per Protocol Set), statistical analyses will not be duplicated or repeated.

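### The Part 2 primary test of Day 190 muscle volume uses a Per Protocol Set defined by post-randomisation events; the all-randomised set is only a repeat

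*SAP*

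**What the plan says.** On the choice of set, SAP 4.7.2.2 (MRI: Total Muscle Volume) states: "The Per Protocol Set will be used for the primary analysis. The analyses described above will also be repeated for the Full Analysis Set". The same instruction follows the other randomised endpoints in that section. The protocol synopsis says of efficacy analyses that "these will be done using the full analysis set and per protocol set populations", with no order between the two. SAP Section 5 records the revised Per Protocol definition but not its primary role.

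On the sets themselves, SAP 4.2 and Protocol 14.1 define the Part 2 Full Analysis Set (FAS) as everyone randomised. SAP 4.1 carries a narrower sentence, limited to participants who were treated and had the correct assignment. SAP 4.2 defines the Per Protocol Set by at least one dose and no major violation, and lists four violations:

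- early exit: "Patients who discontinue the study prior to the Cycle 3 Day 43 visit; these patients are replaced per protocol";
- a Day 1 or Day 190 MRI done at least 7 days after dosing;
- late functional tests: "Patients whose functional assessments (i.e. 10mW/R, mid-level PUL, 6MWT, 4-stair climb) at Day 1 or Day 190 were done 7 or more days" after dosing;
- incomplete dosing: "Patients who did not receive the full study drug administration planned per protocol at all injection sites" on either or both sides, at two or more visits in a row, unless the reason was patient safety or feasibility.

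On replacement, Protocol 10.5 allows it for a patient who "discontinues the study for reasons other than a safety issue related to ACE-083" before completing Day 43. SAP 3.2 has the same rule, for exits with any cause except "a safety issue related to investigational study drug and the patient had not completed the Day 43 visit, the patient may be replaced". SAP 4.1.5 rules out imputation for patients who left before Day 43 and were replaced.

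**The concern.** Part 2 is randomised and placebo-controlled so that its primary objective rests on comparable groups. Protocol Table 6 places randomisation within the 24 hours before the first dose. The one-dose condition and all four listed violations are therefore decided after randomisation, when they may be related to treatment or to outcome. An all-randomised set is already defined, planned and supported by multiple imputation, yet it has second place. If the two analyses disagree, the SAP makes the Per Protocol result the answer.

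Two of the bullets can also discard good primary data. A late functional test does not make the MRI invalid, and a patient with incomplete dosing may still have a valid Day 190 scan. The sample size allows for drop-outs (28 randomised per muscle to leave 12 completers per arm). It makes no allowance for completers removed by the Per Protocol rules.

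**Working it through.** **Inputs.** SAP 4.1.1: difference 10 points, SD 9, two-sided alpha 0.10, 12 v 12 completers per muscle, stated power 83%. The documents give no violation rate, so the number excluded and how those patients differ are assumptions below.

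**Step 1: the plan's own figure.** Two-sample t-test, noncentral t, with noncentrality = 10 / (9 × √(1/n₁ + 1/n₂)).

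| Completers analysed | Noncentrality | df | Power |
|---|---|---|---|
| 12 v 12 | 10/3.674 = 2.72 | 22 | 83.9% |
| 11 v 12 | 10/3.757 = 2.66 | 21 | 82.4% |
| 10 v 12 | 10/3.854 = 2.60 | 20 | 80.5% |

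The first row reproduces the stated 83%. The other two show the cost of losing one or two scans in one arm with no bias at all.

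**Step 2: how the choice of set moves the estimate.** Suppose each arm has 12 completers and the true gain is 10 points. Let m of the ACE-083 completers be excluded, with a gain d points lower. The Per Protocol estimate stays at 10.0 and the FAS estimate is 10 − m × d/12. If the excluded completers are instead on placebo, with a change d points lower, the FAS estimate is 10 + m × d/12.

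- d = 0: 10.0 on both sets.
- m = 1, d = 5, ACE-083: 10 − 5/12 = 9.6.
- m = 1, d = 10, ACE-083: 10 − 10/12 = 9.2.
- m = 1, d = 10, placebo: 10 + 10/12 = 10.8.

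**Step 3: a second route.** SAP 4.7.2.2 imputes Day 190 from the Day 43 and Day 106 values. An excluded patient with those scans but no usable Day 190 scan therefore also shifts the FAS estimate. Patients who leave before Day 43 matter least: under the planned missing-at-random imputation, the two sets would give nearly the same estimate for them.

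**Step 4: simulated power.** 3,000 trials per row, one muscle, 14 v 14 randomised, 2 drop-outs per arm, 20 imputations, ANCOVA with baseline. Cells show estimate/power.

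| Excluded completers | Per Protocol | FAS |
|---|---|---|
| 1 ACE-083, d = 0 | 10.07 / 82% | 10.07 / 83% |
| 1 ACE-083, d = 10 | 9.93 / 80% | 9.09 / 72% |
| 1 placebo, d = 10 | 10.09 / 81% | 10.92 / 86% |

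**Step 5: type I error.** A separate simulation with no true effect (200,000 runs, 14 v 14) excluded two ACE-083 patients. Random exclusion left the error at 10.1%. Exclusion correlated 0.3 or 0.5 with outcome gave 10.7% or 12.0%.

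**Step 6: passages that do not fit together.** SAP 4.2 treats early exits as replaced, while Protocol 10.5 and SAP 3.2 permit replacement only for some of them and do not require it. SAP 4.1 and 4.2 word the FAS differently. At exactly 7 days after the Day 190 dose, SAP 4.1.5 keeps the assessment and 4.2 excludes the patient.

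**The case against.** The choice is prespecified, the period is double-blind, and the same analysis on the FAS is planned, so both results will be available. The dosing bullet already exempts safety reductions and feasibility, which are the reasons most plausibly linked to treatment. The illustrations rest on assumed values, and d = 10 means a complete non-responder. All of this stands, and it limits the seriousness of the point. It does not give the primary result the protection of randomisation.

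A reader might infer three stronger things that the documents do not support.

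- *That the SAP contradicts the protocol.* It does not: the protocol names both sets and ranks neither.
- *That patients who leave early because of study-drug safety are certainly removed.* The early-exit bullet read alone says so. But it also calls these patients replaced per protocol, and the replacement rule covers only exits not caused by study-drug safety. The bullet may mean that smaller group.
- *That valid biceps scans will be lost to late walk tests.* Protocol Table 6 says "lower leg assessments will be collected for the BB cohorts at screening visits, Day 190 and Day 393/EOS only", and the functional-test bullet does not limit itself to the treated muscle, so the literal reading is possible. The SAP, however, analyses the lower-leg tests only for tibialis anterior patients and mid-level PUL only for biceps patients, so a muscle-specific reading is natural. Procedures are also due before dosing, so such a delay would already be a marked deviation.

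**Conclusion.** The point stands as a choice that should be changed, not as an error that invalidates the trial. The primary test is assigned to a set fixed by post-randomisation events, while a set of all randomised patients is available. The finding covers the listed violations; SAP 4.2 introduces them as included items, so the list may not be complete.

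The size is unknown. On the stated assumptions, one atypical excluded completer separates the two estimates by 10/12 = 0.8 points, and one or two lost scans cost 1.5 or 3.4 points of power (83.9 − 82.4 and 83.9 − 80.5). A reader might infer that the Per Protocol Set flatters ACE-083. The documents do not show that: the sign depends on which arm loses patients and how they differ, and there is no bias if exclusion is unrelated to outcome.

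**What to change.** - **SAP 4.7.2.2:** state that the FAS as defined in 4.2 is primary for Day 190 TMV and the Per Protocol Set is supportive. Say explicitly that original and replacement patients are both included, each analysed as randomised. For consistency, make the same change for the other randomised Day 190 endpoints that carry the sentence: calculated contractile muscle volume, fat fraction, calculated intramuscular fat, strength, 10-metre walk/run, 6-minute walk, 4-stair climb, mid-level PUL and FSHD-HI.
- **SAP 4.1:** delete the conflicting FAS sentence.
- **SAP 4.1.5:** remove the bar on imputing replaced patients. This affects every imputed endpoint, not only TMV.
- **SAP 4.2:** apply the late-functional-test bullet only to the analysis of that test. Reconcile the replacement wording with Protocol 10.5, and the 7-day cut-off with SAP 4.1.5.

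The cost is wording and minor re-programming, with no added patients or visits. The headline estimate and power may move either way. With one ACE-083 non-responder excluded, simulated power is 72% on the FAS against 80% on the Per Protocol Set, which is not a trivial loss. If the exclusion falls in the placebo arm, it is 86% against 81%.
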